## List of abbreviations

Abbreviation	Definition
AE	Adverse event
CD	Crohn's disease
CRP	C-reactive protein
eDCF	Electronic data collection form
ENCePP	European Network of Centres for Pharmacoepidemiology and Pharmacovigilance
FRESH	Feraccru® Real World Effectiveness Study in Hospital Practice
GafRECGI	Governance Arrangements for Research Ethics Committees Gastrointestinal
Hb	Haemoglobin
HBI	Harvey-Bradshaw Index
HRA	Health Research Authority
IBD	Inflammatory bowel disease
IDA	Iron deficiency anaemia
ISPE	International Society for Pharmacoepidemiology
IV	Intravenous
MAH	Marketing Authorisation Holder
MCH	Mean corpuscular haemoglobin
MCV	Mean corpuscular volume
MHRA	Medicines and Healthcare Products Regulatory Agency
NHS	National Health Service
OFPs	Oral ferrous products
QoL	Quality of life
R&D	Research and Development
REC	Research Ethics Committee
SADR	Serious adverse drug reaction
SAE	Serious adverse event
SCCI	Simple Clinical Colitis Index
SDV	Source data verification
UC	Ulcerative colitis
WHO	World Health Organization

## **List of definitions**

Baseline is defined as the date of initiation of Feraccru®.

Iron deficiency anaemia is defined by the World Health Organization (WHO) as <12.0 g/dL in women and <13.0 g/dL in men.

Mild to moderate iron deficiency anaemia (secondary to either CD or UC) is also defined in this study as serum ferritin concentration <30 microgram/L or transferrin saturation of <20%.

Normalised haemoglobin (Hb) is defined in this study as Hb  $\geq$ 12.0 g/dL for females and  $\geq$ 13.0 g/dL for males.

Normalised serum ferritin is defined in this study as serum ferritin concentration  $\geq$ 30 microgram/L and  $\leq$ 300 microgram/L.

Normalised transferrin saturation is defined in this study as transferrin saturation between 20% and 50%.

Observation period is defined as 12 weeks after initiation of Feraccru® (permitting a window from 10 to 16 weeks).

## 1. Study synopsis

Title	Feraccru® Real World Effectiveness Study in Hospital Practice (FRESH): A real world study to describe the outcomes associated with the use of ferric maltol (Feraccru®) for the management of iron deficiency anaemia in patients with inflammatory bowel disease in the UK.
Background and rationale for study	
Approximately 20–75% of patients with inflammatory bowel disease (IBD) experience iron deficiency anaemia (IDA), which impacts on patients' quality of life (QoL) through a range of symptoms.
 
Oral ferric maltol (Feraccru®) is a novel iron complex licensed in the UK for the treatment of IDA in patients with IBD. Since its launch in 2016, Feraccru® has been used in some secondary care gastroenterology centres. Due to its high bioavailability and better tolerability compared with ferrous iron salt complexes, Feraccru® is likely to be used in patients after failure of oral ferrous products (OFPs), with the aim of preventing the need for IV iron infusions. In the phase III clinical trial, approximately 70% of patients had normalised haemoglobin (Hb) levels after 12 weeks of treatment with Feraccru®.
 
The aim of the study is to understand the early experiences of Feraccru® in patients with IBD and IDA in the UK, including treatment effectiveness, patterns of use and tolerability. By describing the characteristics of patients treated with Feraccru® and their outcomes, this study will provide the medical community with important information to support treatment decisions for their patients. This will ultimately support improvements to patient care, including the long-term outcomes of patients with IBD and IDA.

Objectives	
Primary objective:
 

• To describe the percentage of patients with normalised Hb levels at 12 weeks after initiation of Feraccru®.

 
Secondary objectives:
 

• To describe the clinical outcomes associated with the use of Feraccru® in the real world, including:

○ Change in Hb levels at 4 and 12 weeks after initiation of Feraccru®

○ Time to normalisation of Hb levels after initiation of Feraccru®

○ Change in serum ferritin levels at 4 and 12 weeks

	
after initiation of Feraccru®
 
 
○ Percentage of patients with normalised ferritin levels at 12 weeks after initiation of Feraccru®
 
○ Time to correction of serum ferritin levels after initiation of Feraccru®
 
○ Change in transferrin saturation at 4 and 12 weeks after initiation of Feraccru®
 
○ Percentage of patients with normalised transferrin saturation at 12 weeks after initiation of Feraccru®
 
○ Time to correction of transferrin saturation after initiation of Feraccru®
 
● To describe the characteristics of patients receiving Feraccru® in the real world, including: 
 
○ Age and sex
 
○ Type of IBD
 
○ Haematology and biochemistry parameters at baseline
 
○ Time from diagnosis of IBD to initiation of Feraccru®
 
○ Time from diagnosis of IDA to initiation of Feraccru®
 
○ Iron treatment history
 
○ Reason(s) for discontinuing each prior oral ferrous product
 
○ Reason(s) for initiating Feraccru®
 
○ Percentage of patients who discontinue Feraccru®
 
○ Reason(s) for discontinuing Feraccru®
 
○ Type, severity and time of adverse events that are related to and caused by (in the clinician's opinion) Feraccru®, from initiation of Feraccru®
 
 
 

Hypothesis statement	As the study is descriptive in nature there is no a priori hypothesis to be tested.
Study design	
An observational, multi-centre cohort study will be conducted in five secondary care gastroenterology centres in the UK.
 
Patients who are prescribed Feraccru® in routine practice will be identified by their care team and approached and asked to provide consent to allow their medical records to be used in the study. There will be no change to the management of patients as a result of taking part in the study. No additional patient investigations or tests will be required.
 
In order to maximise the number of eligible patients, there will be two methods of patient identification and consent:
 
 
● Retrospective recruitment - Patients initiated on Feraccru® since June 2016 will be approached and asked to provide consent either by post, or when they return
 

	
to clinic for routine follow-up visits.
 
 
Prospective recruitment - Patients initiated on Feraccru® during the study period will be identified and asked to provide consent at the time of Feraccru® initiation.
 

Data source(s)	Data will be collected from hospital medical records, by a member of the care team or a researcher in the study centre.
Number of centres	Five secondary care centres in the UK.
Number of subjects	Approximately 100 patients with IBD (Crohn's disease [CD] or ulcerative colitis [UC]) who are also diagnosed with IDA.
Study time period	12 weeks (permitting a window from 10 to 16 weeks to allow for routine follow up clinic visits to occur).
Patient selection	
Inclusion criteria
 
 
Male and female patients aged <math>\geq 18</math> years at the time of initiation
 
Patient presenting with mild to moderate IDA that is secondary to either CD or UC defined as: 
 
Hb <math><12.0</math> g/dL in females
 
Hb <math><13.0</math> g/dL in males
 
Serum ferritin concentration <math><30</math> microgram/L or transferrin saturation of <math><20\%</math>
 
 
 
Patient receiving Feraccru® since the time of UK launch in June 2016
 
 
Exclusion criteria
 
 
Patient receiving Feraccru® as part of an interventional clinical trial
 
Patients with severely active IBD or requiring corticosteroids at the time of initiation on Feraccru®
 
Patient with an IBD flare, as determined by the clinician
 
Patient with medical records that are not available for review
 
Patient not willing or unable to consent to study participation, or patient is deceased at the start of data collection period
 

Study endpoints	
Primary endpoint:
 
 
Percentage of patients with normalised Hb levels at 12 weeks (permitting a window from 10 to 16 weeks) after initiation of Feraccru®
 
 
Secondary endpoints:
 
 
Descriptive analyses summarising change from baseline
 

	
(permitting a window from -2 to 2 weeks) in Hb levels at 4 weeks (permitting a window from 3 to 5 weeks) where data are available, and 12 weeks (permitting a window from 10 to 16 weeks) after initiation of Feraccru®
 
 
• Time to normalisation of Hb levels after initiation of Feraccru®
 
• Descriptive analyses summarising change from baseline (permitting a window from -2 to 2 weeks) in ferritin levels at 4 weeks (permitting a window from 3 to 5 weeks) where data are available, and 12 weeks (permitting a window from 10 to 16 weeks) after initiation of Feraccru®
 
• Percentage patients with normalised ferritin levels at 12 weeks (permitting a window from 10 to 16 weeks) after initiation of Feraccru®
 
• Time to correction of serum ferritin levels after initiation of Feraccru®
 
• Descriptive analyses summarising change from baseline (permitting a window from -2 to 2 weeks) in transferrin saturation at 4 weeks (permitting a window from 3 to 5 weeks) where data are available, and 12 weeks (permitting a window from 10 to 16 weeks) after initiation of Feraccru®
 
• Percentage of patients with normalised transferrin saturation at 12 weeks (permitting a window from 10 to 16 weeks) after initiation of Feraccru®. Normalised transferrin saturation is defined as transferrin saturation between 20% and 50%
 
• Time to correction of transferrin saturation after initiation of Feraccru®
 
• Patient characteristics: age, sex and type of IBD
 
• Descriptive analyses of haematology and biochemistry parameters at baseline
 
• Time from diagnosis of IBD to initiation of Feraccru®
 
• Time from diagnosis of IDA to initiation of Feraccru®
 
• Descriptive analyses of prior IV iron treatment, to include at least the percentage of patients with one or more prior infusions
 
• Reason(s) for discontinuing each prior oral ferrous product
 
• Reason(s) for initiating Feraccru®
 
• Percentage of patients who discontinue Feraccru®
 
• Reason(s) for discontinuing Feraccru®
 
• Type, severity and time of adverse events that are related to and caused by (in the clinician's opinion) Feraccru®, from initiation of Feraccru®
 

--	---

Statistical considerations	
Given the descriptive nature of the study, a preliminary estimation of the required sample size is expressed in terms of precision and not statistical power. The estimated percentage of patients treated with Feraccru® and a reported normalised Hb at 12 weeks is approximately 66%. The accuracy of this point estimate will vary according to the number of participants in the study. Based on this estimate, precision can be calculated using a Binomial confidence interval. With a sample size of 100 patients, the precision of the estimates is between 9–10%. This means that the percentage of patients treated with Feraccru® with a reported normalised Hb at 12 weeks will be within 9–10% of the true population percentage.
 
Data from all centres will be pooled for analysis. The planned analysis will be descriptive in nature.

Regulatory, ethical and administrative obligations	
In line with the harmonised edition of the Governance Arrangements for Research Ethics Committees (GAfREC) (effective from 1st September 2011), this study is required to be submitted for NHS REC review, as it is an observational research study involving collection of non-identifiable information by an external data collector. Consent will be sought from patients and only those who consent will be included in the study.

## **2. Study amendments and protocol deviations**

All amendments to the protocol will be documented in Table 1. Protocol deviations will be documented in a Protocol Deviation Log.

**Table 1 Study amendments**

Amendment number	Date of amendment	Amendment description	Reason for amendment

### 3. Background and rationale

Ulcerative colitis (UC) and Crohn's disease (CD) are both types of inflammatory bowel disease (IBD) that are characterised by symptoms of bloody diarrhoea, abdominal pain and cramps. Anaemia is a complication that occurs in up to 70% of patients with CD or UC. Iron deficiency anaemia (IDA) is the most common cause of anaemia in these patients.

Iron deficiency can result from insufficient dietary intake, chronic inflammation reducing absorption, malabsorption and/or intestinal bleeding. In IBD, iron deficiency results from a combination of functional iron deficiency due to inflammation and chronic blood loss. Approximately 20–75% of patients with IBD experience IDA, which can impair patients' quality of life (QoL) through symptoms such as fatigue, dizziness, headache, tachycardia, shortness of breath, depression, and reduced cognitive functioning. Not only does IDA in IBD have a considerable impact on activities of daily living, but severe symptoms can lead to hospitalisation. Iron deficiency anaemia is defined by the World Health Organization (WHO) as haemoglobin (Hb) <12.0 g/dL in women and Hb <13.0 g/dL in men. Laboratory investigations using modern automated cell counters are able to detect changes in red cell indices, including reduced mean corpuscular volume (MCV) and reduced mean corpuscular haemoglobin (Hb) (MCH), necessary for a diagnosis of IDA.

Treatment goals in the clinical management of IDA are to normalise Hb concentrations and red cell indices, as well as replenishing iron stores. Clinical guidelines recommend the inclusion of oral iron supplementation to correct anaemia, with oral iron continued for 3 months after the IDA has been corrected. Guidance also suggests regular patient monitoring; every 3 months up to a year after IDA correction then 12 months thereafter, and again if symptoms of anaemia develop. For patients who are intolerant, or have an insufficient response to oral iron, intravenous (IV) iron is recommended which is often administered in a hospital setting as a day case. This results in an increased burden on patients and increased costs associated with both the drug and use of hospital services.

Oral ferric maltol (Feraccru®) is a novel iron complex consisting of a single ferric iron ion (Fe3+), chelated with high affinity to three maltol molecules. Maltol is a natural sugar derivative that binds with high affinity to ferric iron until it is released directly into the area of the gastrointestinal (GI) tract where it is best absorbed. This is suggested to confer high

bioavailability and better tolerability compared with ferrous iron salt complexes, due to the reduced exposure of free iron throughout the GI tract. Feraccru® is licensed in the UK for the treatment of IDA in patients with IBD and has been used in a number of secondary care gastroenterology centres since its launch in 2016. Feraccru® is likely to be used in patients after failure of oral ferrous products (OFPs), with the aim of preventing the need for intravenous (IV) iron infusions. In the phase III clinical trial, approximately 70% of patients had normalised haemoglobin after 12 weeks of treatment with Feraccru®.

### **3.1 Rationale for study**

As Feraccru® has only been on the UK market for a relatively short period of time, real world evidence is required to understand early experiences of Feraccru® in IBD patients with IDA in UK routine practice. For example, data are needed to determine whether biochemical outcomes seen in clinical trials can be replicated in a more diverse and representative population in the real world. Information is also needed about the characteristics and treatment history of patients who receive Feraccru®, and the tolerability that is achieved. By describing the characteristics of patients treated with Feraccru® and their associated outcomes, this study will provide the medical community with important information to support their treatment decisions for their patients. The findings from this study will ultimately support improvements to patient care, including the long-term outcomes of patients with IBD and IDA.

## **4. Aim and objectives**

### **4.1 Aim**

To describe the real-world use of Feraccru®, and the characteristics and the clinical outcomes of patients with IBD and IDA who receive Feraccru®.

### **4.2 Primary objective**

To describe the percentage of patients with normalised Hb levels at 12 weeks after initiation of Feraccru®.

#### 4.3 Secondary objectives

- To describe the clinical outcomes associated with the use of Feraccru® in the real world, including:
  - Change in Hb levels at 4 and 12 weeks after initiation of Feraccru®
  - Time to normalisation of Hb levels after initiation of Feraccru®
  - Change in serum ferritin levels at 4 and 12 weeks after initiation of Feraccru®
  - Percentage of patients with normalised ferritin levels at 12 weeks after initiation of Feraccru®
  - Time to correction of serum ferritin levels after initiation of Feraccru®
  - Change in transferrin saturation at 4 and 12 weeks after initiation of Feraccru®
  - Percentage of patients with normalised transferrin saturation at 12 weeks after initiation of Feraccru®
  - Time to correction of transferrin saturation after initiation of Feraccru®
- To describe the characteristics of patients receiving Feraccru® in the real world, including:
  - Age and sex
  - Type of IBD
  - Haematology and biochemistry parameters at baseline
  - Time from diagnosis of IBD to initiation of Feraccru®
  - Time from diagnosis of IDA to initiation of Feraccru®
  - Iron treatment history
  - Reason(s) for discontinuing each prior oral ferrous product
  - Reason(s) for initiating Feraccru®
  - Percentage of patients who discontinue Feraccru®
  - Reason(s) for discontinuing Feraccru®

- Type, severity and time of adverse events that are related to and caused by (in the clinician's opinion) Feraccru®, from initiation of Feraccru®

## **5. Hypothesis**

As the study is descriptive in nature, there is no *a priori* hypothesis to be tested.

## **6. Study design and methodology**

The study has been designed and will be conducted according to the requirements of the European Network of Centres for Pharmacoepidemiology and Pharmacovigilance (ENCePP; <http://www.encepp.eu/index.shtml>) and International Society for Pharmacoepidemiology (ISPE; [https://www.pharmacoepi.org/resources/guidelines\\_08027.cfm](https://www.pharmacoepi.org/resources/guidelines_08027.cfm)) guidance, as appropriate.

This study will be an observational, multi-centre cohort study conducted in five secondary care NHS centres across the UK. Patients will be recruited using both retrospective and prospective approaches.

### **6.1 Study time periods**

Eligible patients will be followed from the time of initiation on Feraccru® for 12 weeks, with a permitted window from 10 to 16 weeks.

### **6.2 Study population**

The study population will be patients under the management of secondary care gastroenterology centres in the UK that are using Feraccru®. Study participants will be required to consent to study participation by the signing of a consent form before any data are collected.

The study sample will be derived from the population of patients with IBD (either CD or UC) who also have a clinically confirmed diagnosis of IDA and were either:

- Initiated on Feraccru® since June 2016 (retrospectively recruited patients), or
- Initiated on Feraccru® during the study period (prospectively recruited patients).

### **6.2.1 Inclusion criteria**

- Male and female patients aged  $\geq$  18 years at the time of initiation
- Patients presenting with mild to moderate IDA that is secondary to either CD or UC, defined as:
  - Hb  $<12.0$  g/dL in females
  - Hb  $<13.0$  g/dL in males
  - Serum ferritin concentration  $<30$  microgram/L or transferrin saturation of  $<20\%$
- Patients receiving Feraccru® since the time of UK launch in June 2016

### **6.2.2 Exclusion (ineligibility) criteria**

- Patient receiving Feraccru® as part of an interventional clinical trial
- Patients with severely active IBD or requiring corticosteroids at the time of initiation on Feraccru®
- Patient with an IBD flare, as determined by the clinician
- Patient with medical records that are not available for review
- Patient not willing or unable to consent to study participation, or patient is deceased at the start of data collection period.

### **6.2.3 Participant recruitment**

Patients who are prescribed Feraccru® and eligible for inclusion in the study will be identified by their care team and approached and asked to provide consent to allow their

medical records to be used in the study. There will be no change to the management of patients as a result of taking part in the study. No additional patient investigations or tests will be required. In order to maximise the number of eligible patients, there will be two methods of patient identification and consent;

1. Retrospective recruitment - Patients who were initiated on Feraccru® since its launch in June 2016 will be approached and asked to complete a consent form either by post or when they return to the gastroenterology clinic for routine follow-up visits.
2. Prospective recruitment - Patients initiated on Feraccru® during the study period will be identified and asked to provide consent (and complete a consent form) at the time of Feraccru® initiation.

The study will recruit approximately 100 patients across 5 centres.

### **6.3 Data collection**

Patients will be identified in all study records using a unique study code, which will allow individual patients to be identified for each of their clinic visits and allow data queries to be raised with centres by the data management team at pH Associates while preserving patient confidentiality. Further information on data collection can be found in section 7.

Data relating to the patient's demographics, IDA treatment history, outcomes, and tolerability of Feraccru®, will be collected by a member of the care team, or a researcher in the study centre. Data will be entered onto electronic (MACRO) data collection forms (eDCF) designed specifically for the study.

### **6.4 Data source**

The study data will be derived from hospital medical records. This will include, but not be limited to case notes, prescribing records, laboratory reports and investigation reports.

## 6.5 Study endpoints and variables

### 6.5.1 Primary endpoint

- Percentage of patients with normalised Hb levels at 12 weeks (permitting a window from 10 to 16 weeks) after initiation of Feraccru® (normalisation of Hb defined as Hb  $\geq$ 12 g/dL for females and  $\geq$ 13.0 g/dL for males)

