### 6.5.2 Secondary endpoints

- Descriptive analyses summarising change from baseline (permitting a window from -2 to 2 weeks) in Hb levels at 4 weeks (permitting a window from 3 to 5 weeks) where data are available, and 12 weeks (permitting a window from 10 to 16 weeks) after initiation of Feraccru®
- Time to normalisation of Hb levels (normalisation of Hb defined as Hb  $\geq$  12 g/dL for females and  $\geq$ 13.0 g/dL for males) after initiation of Feraccru®
- Descriptive analyses summarising change from baseline (permitting a window from -2 to 2 weeks) in ferritin levels at 4 weeks (permitting a window from 3 to 5 weeks) where data are available, and 12 weeks (permitting a window from 10 to 16 weeks) after initiation of Feraccru®
- Percentage of patients with normalised ferritin levels at 12 weeks (permitting a window from 10 to 16 weeks) after initiation of Feraccru®. Normalised serum ferritin is defined as serum ferritin concentration  $\geq$ 30 microgram/L and  $\leq$ 300 microgram/L
- Time to correction of serum ferritin levels after initiation of Feraccru®
- Descriptive analyses summarising change from baseline (permitting a window from -2 to 2 weeks) in transferrin saturation at 4 weeks (permitting a window from 3 to 5 weeks) where data are available, and 12 weeks (permitting a window from 10 to 16 weeks) after initiation of Feraccru®
- Percentage of patients with normalised transferrin saturation at 12 weeks (permitting a window from 10 to 16 weeks) after initiation of Feraccru®. Normalised transferrin saturation is defined as transferrin saturation between 20% and 50%

- Time to correction of transferrin saturation after initiation of Feraccru®
- Patient characteristics: age, sex and type of IBD
- Descriptive analyses of haematology and biochemistry parameters at baseline
- Time from diagnosis of IBD to initiation of Feraccru®
- Time from diagnosis of IDA to initiation of Feraccru®
- Descriptive analyses of prior IV iron treatment, to include at least the percentage of patients with one or more prior infusions
- Reason(s) for discontinuing each prior oral ferrous product
- Reason(s) for initiating Feraccru®
- Percentage of patients who discontinue Feraccru®
- Reason(s) for discontinuing Feraccru®
- Type, severity and time of adverse events that are related to and caused by (in the clinician's opinion) Feraccru®, from initiation of Feraccru®

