### **6.5.3 Variables to be collected**

The following study variables will be collected during the observation period to measure the study endpoints, in order to describe the use of Feraccru® in the real world.

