#### **Patient demographics and other characteristics:**

- Age at initiation of treatment with Feraccru®
- Sex (Male/Female)
- Date diagnosed with IBD
- Type of IBD (CD/UC)
- Date diagnosed with IDA
- Description of IV iron treatment history, to include at least the number of prior infusions
- Description of oral iron treatment history, where available in secondary care notes

- Experience of oral ferrous products (OFPs) (Yes/No), if yes:
- Name(s) of OFP(s)
- Reason(s) for discontinuing OFP(s)

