**Feraccru® treatment:**

- Date initiated on Feraccru®
- Reason(s) for initiating Feraccru®
- Date discontinued Feraccru®
- Reason (s) for discontinuation of Feraccru®

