**Haematology and biochemistry parameters:**

The date(s) and result(s) of haemoglobin (Hb), ferritin and transferrin saturation will be collected from baseline (permitting a window from -2 to 2 weeks) to 12 weeks (permitting a window from 10 to 16 weeks). The date(s) and result(s) of the following haematology and biochemistry parameters will be collected at baseline only (permitting a window from -2 to 2 weeks):

- Folate
- B12
- Mean corpuscular volume
- Mean corpuscular Hb
- Platelets
- C-reactive protein (CRP)

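### The primary endpoint counts any normal Hb at weeks 10–16, and no listed variable commits to recording other iron or transfusion after initiation, so normalisation that followed such treatment can be only partly separated out

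*Combined protocol and SAP*

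**What the plan says.** All references are to the combined protocol and SAP.

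- **Endpoint.** Section 6.5.1 defines the primary endpoint as "Percentage of patients with normalised Hb levels at 12 weeks (permitting a window from 10 to 16 weeks) after initiation of Feraccru", using sex-specific Hb thresholds. It does not require the patient still to be on Feraccru or to have had no other iron or transfusion.
- **Variables.** Section 6.5.3 opens with "The following study variables will be collected during the observation period to measure the study endpoints". Its iron items are "Description of IV iron treatment history, to include at least the number of prior infusions" and "Description of oral iron treatment history, where available in secondary care notes". The matching endpoint in Section 6.5.2 is "Descriptive analyses of prior IV iron treatment, to include at least the percentage of patients with one or more prior infusions". The Feraccru items are the start date, reasons for starting, "Date discontinued Feraccru" and reasons for stopping. For laboratory results, "The date(s) and result(s) of haemoglobin (Hb), ferritin and transferrin saturation will be collected from baseline" through to the week-12 window.
- **Other treatment.** The exclusion criteria (6.2.2) do not mention other iron, and taking part leaves routine care unchanged (6.2.3). Transfusion is not mentioned in the text available.
- **Analysis.** Section 9 is descriptive. Section 9.1 provides complete-case analysis for missing values. Neither says how a patient given other treatment is to be counted.
- **Background.** Section 3 says IV iron is recommended for patients who cannot tolerate oral iron or respond too little to it, and expects Feraccru to be used in the hope of avoiding infusions.

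**The concern.** Feraccru is itself an oral iron. On the protocol's own account of practice, a patient who does badly on it is a candidate for IV iron. If that patient receives IV iron and has a normal Hb at week 12, the plan counts a normalisation after initiation of Feraccru, and the listed data need not show that anything else was given.

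This bears on how the rate will be read. The study title and the synopsis both refer to effectiveness, and Section 3.1 gives as an example of the need whether trial results can be reproduced in routine practice. A reader will be inclined to take the percentage as what Feraccru achieved. Nothing the plan commits to collecting would show how much of it followed Feraccru without other iron or transfusion.

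The same gap reaches the eight secondary endpoints in Section 6.5.2 built on Hb, ferritin and transferrin saturation: three changes from baseline, two percentages normalised and three times to normalisation or correction, for example "Time to correction of serum ferritin levels after initiation of Feraccru".

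**Working it through.** **1. What the listed variables can separate**

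| Situation before the week-12 Hb | Visible from the Section 6.5.3 items? |
|---|---|
| Still on Feraccru, nothing else given | Not distinguishable from the next row |
| Still on Feraccru, with other iron or transfusion | No item commits to it |
| Stopped Feraccru | Yes, from the stop date |
| Type and date of treatment after a stop | Only if a stop reason happens to mention it; no date |

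The lack-of-effect report in Section 12.3 is also only a partial signal, since it is not a record of later treatment.

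**2. The plan's own precision figure**

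Inputs from Section 8 and Table 2: p = 66%, Wald interval. The confidence level is not stated; 95% two-sided is assumed. With n = 1.96² × 0.66 × 0.34 / d², half-widths of 7, 8, 9, 10, 11 and 12 points give 175.92, 134.69, 106.42, 86.20, 71.24 and 59.86. These round up to 176, 135, 107, 87, 72 and 60, exactly as in Table 2. At N = 100 the half-width is 1.96 × √(0.66 × 0.34 / 100) = 9.28 points, which agrees with the stated 9–10%.

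**3. Possible size**

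The documents give no rate of other treatment, so every input here is an assumption:
- r, the share of patients given other iron or transfusion before the Hb: 5, 10, 15 or 20%
- s, the share of those who normalise: 60 or 80%
- c, the share of those who would have normalised on Feraccru alone: 10, 30 or 50%

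The observed rate is taken as 66%. The gross contribution is r × s. The net excess is r × (s − c). Leaving such patients out gives (66 − r × s) / (100 − r), with r and r × s in percentage points.

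| r, s | Gross (points) | 66% less gross | Net, c = 10 | Net, c = 30 | Net, c = 50 | Left out |
|---|---|---|---|---|---|---|
| 5, 60 | 3 | 63% | 2.5 | 1.5 | 0.5 | 66.3% |
| 5, 80 | 4 | 62% | 3.5 | 2.5 | 1.5 | 65.3% |
| 10, 60 | 6 | 60% | 5 | 3 | 1 | 66.7% |
| 10, 80 | 8 | 58% | 7 | 5 | 3 | 64.4% |
| 15, 60 | 9 | 57% | 7.5 | 4.5 | 1.5 | 67.1% |
| 15, 80 | 12 | 54% | 10.5 | 7.5 | 4.5 | 63.5% |
| 20, 60 | 12 | 54% | 10 | 6 | 2 | 67.5% |
| 20, 80 | 16 | 50% | 14 | 10 | 6 | 62.5% |

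The net excess runs from 0.5 to 14 points. It exceeds 9.28 in 3 of 8 cases at c = 10, in 1 of 8 at c = 30 and in none at c = 50, which is 4 of 24 in all. Leaving such patients out moves 66% by +1.5 to −3.5 points and never exceeds 9.28. Both the direction and the size depend on the counting rule, which is the reason to fix one in advance.

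**The case against.** The strongest reply is that nothing is wrong with the endpoint. The aim in Section 4.1 is descriptive, Section 5 states no hypothesis, no comparison with 66% is planned, and the title goes on to speak of describing outcomes associated with use. A percentage regardless of other treatment is a proper answer to that aim. This stands, and the percentage should remain primary. It does not remove the need to say what the figure includes.

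The second reply is that the wording leaves room. Section 6.5.3 speaks of collection during the observation period and sets only a minimum for IV iron, and neither the eDCF nor the Data Collection Guidelines are among the documents. This is fair: the fields may exist. But the protocol does not commit to them, and its terms (history, prior) point to treatment before initiation.

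The third reply is that the split can be made already. A reader might infer from the gap that normalisation after other treatment cannot be separated at all. The documents do not support that: stop dates and dated laboratory results allow an on-drug and off-drug split, and failure on Feraccru would often involve stopping it. What stays hidden is treatment given alongside Feraccru and the type of treatment after a stop.

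A reader might also infer that the information would be lost for good. That is not supported either. Records stay at the Trusts, study codes allow queries to centres (6.3, 7.2), and each centre keeps a patient log (15.4). A second pass would cost effort, and Table 3 has analysis beginning in August 2017, the month data collection ends.

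**Conclusion.** The point holds as a gap in what is collected and labelled, not as an error in the primary percentage. The plan counts any normal Hb at weeks 10–16, commits to no record of other iron or transfusion after initiation, and gives no counting rule for such patients. The rate alone therefore does not support a reading as Feraccru effectiveness.

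A reader might infer that the rate is materially inflated. The documents cannot show that. They give no frequency of other treatment, and the 5–20%, 60–80% and 10–50% ranges used here are assumptions. Under them the net excess lies mostly within the planned half-width. The gross 3 to 16 points is an upper reading, because it includes patients who would have normalised on Feraccru anyway.

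Confidence is high on the textual gap and low on its size. It should be fixed because the change is cheap and easiest to make before abstraction.

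**What to change.** **Section 6.5.3 and the eDCF.** Add the type and date of any IV iron or red-cell transfusion, and of other oral iron where secondary care notes show it, from initiation to the Hb used for the primary endpoint. Use the not-known code of Section 7.2 where the record is silent.

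**Section 9.**
1. Keep the planned percentage as primary, labelled as regardless of other treatment or discontinuation.
2. Report how many patients were given other treatment and how many are not known.
3. Add one sensitivity analysis that counts patients given such treatment before that Hb as not normalised on Feraccru, and state how not-known patients are counted in it.
4. Show patients who stopped Feraccru separately; this needs no new field.
5. Apply the same rule to the ferritin and transferrin saturation percentages.

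**Reporting.** Limit effectiveness wording to what both figures support.

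**Cost.** A few dated fields from records already being abstracted (Section 6.4) and a few table rows. Oral iron obtained outside hospital will be captured incompletely: if 10% of patients were not known and 66% of them normalised (both assumed), counting them as treated rather than untreated would move the sensitivity figure by 0.10 × 66 = 6.6 points. That figure may also understate the Feraccru effect, since some of these patients might have normalised on Feraccru alone. Patient care and the sample size do not change.
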